#### **Run-in (Visit 0, week -4)**

At the baseline visit (- 4 weeks), subjects will be deemed eligible for the study after the clinical diagnosis bronchiectasis has been made, and the study has been explained to them. The following procedures will be completed:

- Verify inclusion/exclusion criteria
- Obtain written informed consent (alternatively at visit 1)
- Record medical history
- Collection of demographic information, concurrent disease, concomitant medication use, and previous course(s) of antibiotic therapy in the preceding year
- Physical examination (including sputum characteristics, cough, dyspnoea, pleuritic chest pain, chills or rigors, and lung sounds) and vital signs (respiratory rate, heart rate, blood pressure, body temperature and oxygen saturation)
- Laboratory examination (CRP, Hb, WBC, Sodium, Potassium, Creatinin, eGFR, Liver Function Tests, extra blood sample(s) will be taken and frozen for future research)
- Sputum culture (semi-quantitative)
- Randomisation (or at visit 1)

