### 3. STUDY DESIGN

This study will be set up as a randomized, placebo controlled, multicenter study to evaluate the efficacy and safety of Tobramycin Inhalation Solution (TIS) compared to placebo. The target group are patients with non-CF bronchiectasis with recurrent exacerbations ( $\geq 2$  per year) and colonized by Gram-negative bacteria (including *Haemophilus influenzae*) and/or *Staphylococcus aureus* in sputum. A sufficient number of subjects across 6 sites will be enrolled to ensure 58 patients. These patients are randomized in a 1:1 ratio of TIS OD (29 patients) to placebo OD (29 patients). The study will compare the number of exacerbations for 52 weeks, as well as the other secondary endpoints.

During the study patients visit the outpatient ward. During these visits' actual medical history, physical examination and questionnaires are obtained. Next to these sputum examination, spirometry and safety tests (lab examination, diary card) are performed. Study medication starts after the run-in period.

This study will consist of an up to 30-day screening phase, a treatment phase of 52 weeks, and a washout phase of 4 weeks.

Participating patients are randomized to one of the two study arms and will be treated for at least 9 months and up to 12 months in a double-blind fashion with placebo or TIS 300mg OD. Sputum samples will be collected from each subject for culture. At the Screening Visit (Visit 0) subjects will review and sign the informed consent form (ICF) and the screening procedures will be completed. Subjects meeting all study eligibility criteria will be randomized 1:1 to receive once daily inhaled treatment with either TIS OD or placebo. Subjects will have a screening visit and 6 additional scheduled visits during the study. Subjects will receive their first dose of study drug at the study site on day 1 during visit 1, and on day 7 they will be contacted by phone for the assessment of compliance and tolerance with study drug. Further visits are scheduled with 12-week intervals. Visit 7, which is the final visit of the study, will be conducted 4 weeks after the end of treatment period (see figure 1). At visit 1, subjects will be instructed on daily study drug administration by self-administering study drug under the supervision of study personnel at the site; subjects will self-administer study drug during the complete study period.

[figure not shown]

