## **7.3 Study procedures**

Patients with bronchiectasis and who fulfil the inclusion and exclusion criteria will be asked to participate in the study. After a run-in period of 4 weeks' patients will be randomized to receive one of the two possible treatment regimens: TIS OD 300 mg daily or placebo. Administration will be continuous for the full 12 months. According to the parallel group design patients will be treated for 52 weeks. After completing the intervention period patients will have a follow-up (wash out period) of 4 weeks. This wash-out period was considered to be one month, in which time the antimicrobial effect of the antibiotic supposedly disappears, as suggested in earlier studies.

Subjects will be evaluated at run-in = visit 0 (week -4), visit 1 (day 1- start of the study), visit 2 (week 13), visit 3 (week 26), visit 4 (week 39), visit 5 (week 52: end of treatment) and visit 6 (run-out; week 56: end of the study). One week after start of treatment a phone call will be scheduled. Clinical, laboratory, and bacteriology evaluations will be determined according to the schedule (Figure 1: study schedule). Subjects who terminate treatment should be followed for the same period as those who complete the study, according to the study schedule.

During the study any changes in medical condition and compliance with medication will be filed in the diary card.

At visit 1, after randomisation, a tolerance test with either TIS or placebo (blinded according to randomisation) will be performed. Before nebulizing TIS patients are treated with salbutamol 200mcg using an AeroChamber. During tidal breathing patients inhale 300mg TIS or placebo (at room temperature) by using the Innospire Deluxe nebulizer with mouthpiece during approximately 5 minutes. If patients develop a moderate-severe bronchial obstruction, patients are excluded from the study. The severity of bronchial obstruction and coughing is assessed by a specialized nurse, the respiratory physician or the own GP. An exacerbation is defined as the presence of three or more of the following symptoms or signs for at least 24 hours: increased cough, increased sputum volume, increased sputum purulence, haemoptysis, increased dyspnoea, increased wheezing, fever (>38.5°C)

or malaise, and the treating physician agreed that antibiotic and/or prednisolone therapy was required.

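### The visit 0 list allows randomisation four weeks before day 1 and consent as late as visit 1, contradicting other sections and preceding the month that several eligibility criteria cover

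*Combined protocol and SAP*

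**What the plan says.** The visit 0 list in section 7.3 (week -4) contains "Verify inclusion/exclusion criteria", "Obtain written informed consent (alternatively at visit 1") and "Randomisation (or at visit 1"). Its laboratory line adds that "extra blood sample(s) will be taken and frozen for future research".

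Other parts of the protocol set different timings:

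- **Randomisation.** The opening text of section 7.3 says: "After a run-in period of 4 weeks' patients will be randomized to receive one of the two possible treatment regimens". Section 3 names no visit for randomisation but limits it to subjects who meet every eligibility criterion.
- **Consent.** Section 3 says: "At the Screening Visit (Visit 0) subjects will review and sign the informed consent form (ICF"). Section 10.1 requires consent before any procedure or test specific to the study. Section 10.2 has it signed at an outpatient appointment without saying which visit that is.
- **Start of the study.** Section 7.3 defines it as "visit 1 (day 1- start of the study"). Inclusion 5 (section 4.2) and exclusions 1, 4, 5, 6 and 13 (section 4.3) all look back one month from that start.
- **Day 1.** The visit 1 list collects medical history, concomitant medication and earlier antibiotic courses. It lists no eligibility decision, no consent and no randomisation.

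**The concern.** A site that uses the visit 0 options can follow the visit list and still break the rest of the protocol. It can randomise before the run-in that is supposed to come first, and it can draw and freeze research blood before the patient has consented. Read literally, the two options together even allow randomisation before consent.

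The statistical consequence comes from the analysis sets. Section 9.3.1 puts every randomised patient in ITT. A patient randomised at week -4 who exacerbates or needs antibiotics before day 1 no longer meets the criteria but cannot leave ITT. If never dosed, that patient has not passed the tolerance test and falls outside mITT (section 9.3.2). If dosed, the eligibility criteria have been breached. Randomising only after a day 1 check avoids both outcomes.

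**Working it through.** **Randomisation.** The visit 0 list permits week -4, while the text above it permits only the time after the run-in. A later phrase in section 7.3, which places the tolerance test at visit 1 after randomisation, fits either timing and does not settle the matter.

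**Consent.** The visit 0 list permits visit 1. Section 3 says visit 0, and section 10.1 says before any study-specific procedure. The frozen sample is study-specific and is taken at visit 0, so a site that defers consent cannot satisfy both the list and section 10.1.

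**Eligibility.** The look-back month ends on day 1 and the only listed check is at week -4. At that point almost none of the month has elapsed, so the six criteria cannot be confirmed.

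**Scale.** The plan gives no figure for this, so there is none to reproduce. The inputs are from section 4.4: placebo mean 2.1 exacerbations per year (SD 1.6) and azithromycin mean 0.8 per year. The run-in is 28 days. It is an assumption that these rates hold in the run-in. At a constant rate r per year,

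P(at least one exacerbation) = 1 − exp(−r × 28/365.25).

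- r = 2.1: the mean is 2.1 × 28/365.25 = 0.1610, so P = 1 − exp(−0.1610) = 0.149, or 14.9%.
- r = 0.8: the mean is 0.8 × 28/365.25 = 0.0613, so P = 1 − exp(−0.0613) = 0.059, or 5.9%. This is a low-end assumption, shown because macrolide users may enter.
- r = 3.0, a high-end assumption not taken from the plan: the mean is 3.0 × 28/365.25 = 0.2300, so P = 1 − exp(−0.2300) = 0.205, or 20.5%.

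Allowing for variation between patients, the SD of 1.6 gives a dispersion α = (1.6² − 2.1)/2.1² = 0.46/4.41 = 0.1043. The negative binomial probability is then 1 − (1 + 0.1043 × 0.1610)^(−1/0.1043) = 0.148, or 14.8%. Overdispersion therefore makes almost no difference here.

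Each figure applies per patient actually randomised at visit 0, and that share could be anywhere from 0 to 100%.

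**The case against.** The strongest reply is that the safeguard already exists. Section 3 randomises only patients who meet all criteria, section 7.3 makes day 1 the start of the study, and the day 1 list gathers the necessary history. On that reading the visit 0 entry is a stray permission. This is fair as to intent, but the permission is operative text, and a site following it would randomise before the criteria can be known.

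The absence of a day 1 check is judged from the visit lists alone. Section 7.3 also says: "Clinical, laboratory, and bacteriology evaluations will be determined according to the schedule (Figure 1: study schedule"). That figure is not available in the copy reviewed and may show a day 1 check. This limits the eligibility point, but the figure could not remove the conflicting wording at visit 0.

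Section 3 allows screening of up to 30 days, so the gap may be shorter than 28 days. Part of the month could then be checked at visit 0, and the percentages would fall. The remainder would still be unknown.

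On consent, Appendix 4 describes the blood tests and sputum cultures as part of regular check-ups. That may cover those tests, but it does not cover a sample frozen for research or randomisation itself. Section 10.2 is compatible with either timing and adds nothing to the conflict.

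Finally, the percentages count exacerbations only and borrow rates from another trial. Patients who are free of exacerbation at visit 0 may differ, and no bias in the treatment comparison has been shown. All of that stands.

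**Conclusion.** The point holds and should be corrected. Two contradictions are certain from the text: the visit 0 list against the opening of section 7.3 on randomisation, and the same list against sections 3 and 10.1 on consent. It is equally clear that criteria covering the month before day 1 cannot be fully confirmed at visit 0. Whether a day 1 re-check is missing altogether depends on the schedule figure.

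The size is conditional. At the plan's placebo rate, about 15% of patients randomised at visit 0 would have an exacerbation before day 1, and 5.9% at the azithromycin rate. Both assume a 28-day gap and that those rates apply in the run-in. How many patients were or will be randomised at visit 0 is not stated, so no effect on power or on the treatment estimate is claimed.

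**What to change.** In the visit 0 list, delete the randomisation line and the bracketed alternative after consent, so that consent precedes every visit 0 study procedure. In the day 1 list, add two lines before the tolerance test:

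1. Re-check inclusion 5 and exclusions 1, 4, 5, 6 and 13, together with the visit 0 culture result if that sample is the one qualifying the patient under inclusion 7.
2. Randomisation.

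Align the schedule figure if it differs.

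This applies to patients not yet randomised. Section 4.4 describes additions after an interim analysis, so some of the 58 are already enrolled. For anyone already randomised at visit 0, keep them in ITT as section 9.3.1 requires. Report by arm how many were never dosed and how many were dosed although a criterion was no longer met.

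The cost is two deletions and two added lines, handled as an amendment under section 11.3. No visit or assessment is added, because day 1 already collects the history needed. The practical burden is logistical. Envelopes are held at one hospital (section 7.2) and the investigator delivers study drug to the centres (section 6.8), so both must be available for visit 1 at each site on the day. The protocol already allows randomisation at visit 1, but does not show that every site does it.

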#### **Day 1 (Visit 1)**

- Record medical history
- Assessment of LRTI-VAS
- Quality of Life-Bronchiectasis (QOL-B) questionnaire
- Leicester cough score
- Physical examination (including sputum characteristics, cough, dyspnoea, pleuritic chest pain, chills or rigors, and lung sounds) and vital signs (respiratory rate, heart rate, blood pressure, body temperature and oxygen saturation)

- Collection of demographic information, concurrent disease, concomitant medication use, and previous course(s) of antibiotic therapy in the preceding year
- Spirometry according to the standard criteria of the European Respiratory Society
- Concomitant medication monitoring
- Study drug and Innospire deluxe dispensation
- Inhalation tolerance test with either TIS or placebo (depending on randomisation) and first dose of study drug administered under supervision of study staff
- Instructions on proper administration and return of study drug and proper care of the nebulizer
- Diary card instruction

**Week 1 (Phone call)**

- AE assessment of site effects of study medication
- Assessment compliance with medication and potential problems with nebulizer
- Diary card check

**Week 13 (Visit 2)**

- Record medical history (exacerbation, antibiotics?)
- Diary card check
- Repeat laboratory examination (CRP, Hb, WBC, Sodium, Potassium, Creatinin, eGFR, Liver Function)
- Potential side effects will be recorded
- Dispense study medication
- Remaining study drug is collected and/or is sent to Noordwest Ziekenhuisgroep, location Alkmaar

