**Nature and extent of the burden and risks associated with participation, benefit and group relatedness:** After informed consent patients have 3 monthly visits. During the visits patients have to deliver a sputum sample, fill in the QoL questionnaires and a spirometry will be performed according the study schedule. Also a blood sample will be taken during the visits. All patients are instructed to use the nebulizer adequately. The whole procedure of TIS (preparation, inhalation and cleaning) takes approximately 15 minutes. Adverse effects consist of cough, wheezing and dyspnoea. In general practice salbutamol is used before nebulizing TIS, to relieve these symptoms. TIS has already been used by a number of patients with bronchiectasis and is well tolerated. Safety of TIS will be assessed during each contact.

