Efficacy parameters will include assessment of pulmonary exacerbations, spirometry, LTRI-VAS, QOL-B and Leicester cough questionnaires. Microbiological response measurements will include semi-quantitative density of pathogens in sputum, including the tobramycin minimum inhibitory concentration (MIC) for isolated pathogens. Safety parameters will include assessment of AEs, serial spirometry findings, clinical laboratory test results, vital signs measurements, physical examination. Study drug is dispensed on the regular visits. The first patients will be enrolled in the summer of 2016, with a treatment period of 12 months, we expect to terminate the study 31-01-2020.

In subjects who experience a pulmonary exacerbation, every effort should be made to continue their allocated inhaled study drug, unless the study drug is not tolerated, or the pulmonary exacerbation is believed to be related to study drug. All subjects who receive any study drug need to complete the visit 7 assessments. Subjects who are prematurely withdrawn from study drug will be encouraged to

remain in the study and attend subsequent study visits; at a minimum, they should complete the visit 7 assessments as an early termination visit.

An independent expert will be established to conduct periodic reviews of subject safety for this protocol. The independent expert will also perform a blinded analysis of the pulmonary exacerbation data to check whether the assumptions for sample size estimation are valid, and if they are not, the sample size may be increased.

This study will be conducted in the Noordwest Ziekenhuisgroep, Canisius ZH Nijmegen, Spaarne Gasthuis Hoofddorp, Zuyderland MC Heerlen, VU Medical Center Amsterdam and UMC Utrecht.

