### 4.3 Exclusion criteria

A potential subject who meets any of the following criteria will be excluded from participation in this study:

1. Any exacerbation within the month prior to the start of the study
2. Diagnosis of cystic fibrosis
3. Active allergic bronchopulmonary aspergillosis (ABPA)
4. Any oral, IV or inhaled antibiotics (except for macrolides) within 1 month prior to the start of the study
5. Any IV or IM corticosteroids or change in oral corticosteroids ( $>$  10 mg) within 1 month prior to the start of the study
6. Any change/start treatment regimens macrolides, hypertonic saline, inhaled mannitol or other mucolytics, corticosteroids within 1 month prior to the start of the study
7. Severe immunosuppression or active malignancy
8. Active tuberculosis
9. Chronic renal insufficiency (eGFR  $<$  30 ml/min)
10. Use of loopdiuretics, urea or mannitol
11. Earlier diagnosed hearing impairment, balance disorders or neuromuscular disorders

12. Serious active haemoptysis
13. Have received an investigational drug or device within 1 month prior to the start of the study
14. Serious or active medical or psychiatric illness
15. Pregnancy and child bearing
16. History of poor cooperation or non-compliance
17. Unable to use nebulizers
18. Allergic for tobramycin or NaCl 0.9%

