#### **6.4 Summary of known and potential risks and benefits**

Maintenance use of TIS UPS is generally well tolerated as shown during two clinical studies in 258 cystic fibrosis patients ranging in age from 6 to 48 years. Patients received tobramycin inhalation solution in alternating periods of 28 days on and 28 days off drug in addition to their standard cystic fibrosis therapy for a total of 24 weeks. No severe adverse effects were recorded. The most common side effects are coughing, sore throat, dysphonia and bronchospasm. Tinnitus (3%) was transient, resolved without discontinuation of the tobramycin inhalation solution treatment regimen, and were not associated with loss of hearing in audiograms.

Nine (3%) patients in the tobramycin inhalation solution group and nine (3%) patients in the placebo group had increases in serum creatinine of at least 50% over baseline. In all nine patients in the tobramycin inhalation solution group, creatinine decreased at the next visit.

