#### c. Can the primary or secondary mechanism be induced in animals and/or in ex-vivo human cell material?

Not applicable.

d. Selectivity of the mechanism to target tissue in animals and/or human beings

Not applicable.

e. Analysis of potential effect

see section 6.1, 6.2 and 6.3.

f. Pharmacokinetic considerations

see section 6.1 and 6.2.

g. Study population

non-CF bronchiectasis.

h. Interaction with other products

Combination with furosemide, ureum or mannitol should be avoided because of potential nephro- and/or ototoxicity. Especially, nephrotoxicity may occur in combination with IV prescribed aminoglycosides, amphotericin B, cephalosporins, polymyxins, ciclosporin, tacrolimus and platinum containing drugs. A combination with botulinetoxine or anticholinesterases (e.g., neostigmine, pyridostigmine) may induce a prolonged neuromuscular blockade.

i. Predictability of effect

Effect can possibly be measured by biomarkers (inflammation), lung function and bacterial load in sputum.

j. Can effects be managed?

Not applicable.

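### No written visit list asks about tinnitus, hearing or balance, week 56 has no side-effects item, and 8.2.1 contradicts itself on whether unrelated adverse events are recorded

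*Combined protocol and SAP*

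**What the plan says.** **Recognition of the risk.** Section 12.1 h says that combination with certain drugs "should be avoided because of potential nephro- and/or ototoxicity". Section 6.4 reports from two cystic fibrosis studies of 24 weeks, with alternating 28-day periods on and off drug: "Tinnitus (3%) was transient, resolved without discontinuation of the tobramycin inhalation solution treatment regimen". It adds that audiograms showed no associated hearing loss.

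**Safeguards at entry.** Exclusion 11 reads "Earlier diagnosed hearing impairment, balance disorders or neuromuscular disorders". Exclusion 10 bars loop diuretics, urea and mannitol, and 5.2 prohibits them. Visit 0 includes "Verify inclusion/exclusion criteria".

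**Exposure and safety parameters.** Patients are "treated for at least 9 months and up to 12 months". Section 3 states: "Safety parameters will include assessment of AEs, serial spirometry findings, clinical laboratory test results, vital signs measurements, physical examination".

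**Collection.** Visits 0 and 1 take medical history and concurrent disease. The week 1 call has a general adverse-event assessment. Weeks 13, 26, 39 and 52 list "Potential side effects will be recorded". The diary takes any change in medical condition (7.3). The summary says "Safety of TIS will be assessed during each contact".

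**Recording and follow-up.** Section 8.2.1 gives two rules in succession: everything volunteered by the subject or noticed by staff is recorded; then only events related to procedures or medication are recorded and reported yearly. Section 8.4 has all adverse events followed until they abate or stabilise. Section 8.5 gives the independent expert results split by arm, and 11.2 has all adverse events analysed periodically.

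**The concern.** A trial of up to a year of an inhaled aminoglycoside should be able to say, by arm, how many patients developed tinnitus, a hearing complaint or a balance complaint. As written, first detection depends on a general side-effects entry, the diary or a spontaneous report, with no fixed answer before the first dose. A count of zero could then mean that nobody had the complaint or that it did not come up, and a complaint first noted on treatment might have been present before.

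Two textual defects add to this. The only scheduled visit after the end of treatment has no side-effects item, although Appendix 4 rests its negligible-risk classification partly on tinnitus disappearing once the drug is stopped. And the second rule in 8.2.1 would pass the safety comparison through a judgement of relatedness before anyone sees it by arm.

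**Working it through.** **1. The contacts side by side (7.3).**

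| Contact | General route for side effects | Tinnitus, hearing or balance named |
|---|---|---|
| Visit 0 | history, concurrent disease, exclusion check | only through exclusion 11 (diagnosed disorders) |
| Visit 1 | history, concurrent disease | no |
| Week 1 call | adverse-event assessment, diary check | no |
| Weeks 13, 26, 39, 52 | side-effects item, history prompt on exacerbation and antibiotics, diary check | no |
| Week 56 | same history prompt and diary check; no side-effects item | no |

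The named physical-examination items are respiratory or infective, plus vital signs. The three questionnaires in Appendices 1 to 3 have no hearing or balance item. By contrast, creatinine and eGFR are scheduled at visit 0 and at weeks 13, 26, 39, 52 and 56. Of the two toxicities that 12.1 h names together, one has a schedule and the other does not.

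**2. The two rules in 8.2.1.** Take a non-serious tinnitus complaint that the physician judges unrelated.
- First rule: recorded, so available to the expert (8.5) and to the analysis in 11.2.
- Second rule, read literally: not recorded, so absent from both.

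A complaint meeting the seriousness criteria is reported under 8.2.2 either way.

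**3. How many cases to expect.** The plan computes no figure on this point, so there is none to reproduce. Inputs: 29 patients on tobramycin (section 3) and a tinnitus rate of 3% (6.4). The calculation assumes that this rate applies here and that all 29 are dosed and every case is captured.
- Expected cases: 29 × 0.03 = 0.87.
- Chance of none: (1 − 0.03)^29 = 0.97^29 = 0.413, or 41%.
- Exact two-sided 95% upper limit for 0/29: 1 − 0.025^(1/29) = 0.119, or 11.9%.

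The 3% comes from another population and regimen. Over an assumed range of 1% to 10%, the chance of none runs from 0.99^29 = 75% to 0.90^29 = 5%.

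**4. Size of the remedy.** Visit 1, the week 1 call and visits 2 to 6 make 1 + 1 + 5 = 7 contacts; 7 × 58 patients = 406 entries at most.

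**The case against.** The strongest reply is that the generic routes are adequate. The summary promises a safety assessment at each contact, and side-effect recording is a scheduled item on treatment. Tinnitus is a named risk in 6.4 and Appendix 4, so staff may well ask. The schedule figure, diary card and e-CRF are not available, so a prompt there cannot be ruled out. Much of this stands: the documents do not show that nobody asks. They show only that no written visit list requires it.

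On 8.2.1, the second rule can be read as limiting the annual report, and 8.4 and 11.2 both speak of all adverse events. That is probably the intention. The sentence nevertheless restricts recording as well as reporting, and a site could follow it as written.

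It is also true that hearing is neither an objective nor an endpoint, and that 29 patients cannot confirm or refute a 3% rate.

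A reader might infer more than the documents support:
- **That ototoxicity is ignored.** Exclusions 10 and 11 address it, and 6.4 reports no audiogram loss.
- **That a patient must first suspect the drug.** The diary takes any change in condition, and 8.2.1 defines adverse events irrespective of relation.
- **That recovery goes untracked.** Section 8.4 requires follow-up once an event is noted; only first detection depends on the route of capture.
- **That zero recorded cases would conceal a rate well above 11.9%.** This needs a capture fraction, and the documents give none.
- **That longer dosing makes the risk exceed 3%.** Treatment here is longer and continuous but once daily, in a different disease. The documents do not settle the direction.

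**Conclusion.** The point holds as a minor gap in safety ascertainment with three parts: no fixed question on tinnitus, hearing or balance in any written visit list; no side-effects item at week 56 despite the summary; and two incompatible recording rules in 8.2.1. The last two are plain from the text. The first is subject to what the diary card and e-CRF contain.

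The size is modest. Even with full capture, under one case is expected at the 6.4 rate and none is seen 41% of the time; the 11.9% limit for 0/29 easily includes 3%. These figures assume that the cystic fibrosis rate carries over and that all 29 patients are dosed and followed. They do not show that harm is being missed. With so few events expected, one unasked or unrecorded complaint changes the table. The gain from acting is a count by arm in which none means asked and denied.

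**What to change.** 1. **Reword 8.2.1** so that every adverse event is recorded whatever its judged relation, and confine the related-only restriction to the annual report. Reword rather than delete, because the sentence also carries the yearly reporting provision.
2. **Add the side-effects item to the week 56 list.**
3. **Add one fixed yes/no question** on tinnitus, hearing and balance, with start date and whether still present, at visit 1 before the first dose, at the week 1 call and at visits 2 to 6. Ask patients who stop treatment on the same schedule (7.6). Tabulate by arm as present before first dose, new on treatment, and still present at week 56, with exact 95% limits, for the independent expert and the final report. If the e-CRF or diary already asks, say so in 7.3 instead.

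For patients already on treatment, ask at the next contact and flag the baseline as missing. Section 4.4 reads as though the interim analysis has taken place, so missing baselines may be numerous and should be shown as such.

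**Cost.** At most 406 short entries and a few more minor reports in both arms; no new visit or test. A question finds complaints, not silent hearing loss. Audiometry is a clinical decision and is not requested here.
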